7. STATISTICAL METHODS AND DETERMINATION OF SAMPLE SIZE

The main objective will be assessed by calculating descriptive statistics for safety endpoints and by exploratory PK analyses. The PK, safety and efficacy endpoints as well as other assessments as stated in [Section 5](#), will be compared between the treatment groups using descriptive statistics.

7.1 NULL AND ALTERNATIVE HYPOTHESES

No confirmatory testing is performed and hence no null and alternative hypotheses are defined. A justification of the sample size is provided in [Section 7.5](#).

Any confidence intervals computed are to be interpreted in the perspective of the exploratory character of the study; i.e., confidence intervals are considered as interval estimates for effects.

7.2 PLANNED ANALYSES

7.2.1 General considerations

The following analysis sets will be defined for this trial:

- Treated Set (TS):
The Treated Set (TS) consists of patients who are randomised to a treatment group and receive at least one dose of study medication.
- Per Protocol Set (PPS):
The Per Protocol Set (PPS) will consist of patients from TS considering exclusion from the set based on important protocol deviations.
- Pharmacokinetic Parameter Analysis Set (PKS):
The Pharmacokinetic Parameter Analysis Set (PKS) includes all patients in the Treated Set (TS) who provide at least one PK endpoint that was not excluded due to a protocol deviation relevant to the evaluation of PK or due to PK non-evaluability (as specified in the following subsection ‘Pharmacokinetics’). Thus, a patient will be included in the PKS, even if he/she contributes only one PK parameter value for one period to the statistical assessment.

Descriptive and model based analyses of PK parameters will be based on the PKS. All other analyses will be based on the TS.

Pharmacokinetics:

The pharmacokinetic parameters listed in [Section 2.1](#) and [Section 2.2](#) for nintedanib will be calculated using Phoenix WinNonlin™ software (version 6.3 or higher, [REDACTED]) or SAS® Version 9.4 (or later version) by means of noncompartmental analysis and according to the relevant SOP of the sponsor.

Plasma concentration data and parameters of a subject will be included in the PK analyses, if they are not flagged for exclusion due to a protocol deviation relevant to the evaluation of PK (to be decided no later than in the Blinded Report Planning Meeting) or due to PK non-evaluability (as revealed during data analysis, based on the criteria specified below). Exclusion of a subject's data will be documented in the CTR.

Patients who are considered as not evaluable will be listed with their individual plasma concentrations and individual pharmacokinetic parameters. However they will not be included in descriptive statistics for plasma concentrations, pharmacokinetic parameters or other statistical assessment apart from safety evaluation.

Plasma concentrations will be plotted graphically versus time for all patients as listed in the drug plasma concentration-time tables. Only concentrations within the validated concentration range and actual sampling-times will be used for the calculation of pharmacokinetic parameters. For the presentation of the mean profiles, the arithmetic mean and the planned blood sampling times will be used.

Handling and derivation of pharmacokinetic parameters will be done according to BI standards.

The following descriptive statistics will be calculated for analyte concentrations as well as for all pharmacokinetic parameters: N, arithmetic mean, standard deviation, minimum, median, maximum, arithmetic coefficient of variation, geometric mean and geometric coefficient of variation. The data format for descriptive statistics of concentrations will be identical with the data format of the respective concentrations (i.e. three significant digits). The descriptive statistics of pharmacokinetic parameters will be calculated using the individual values with the number of decimal places as provided by the evaluation program. Then the individual values as well as the descriptive statistics will be reported with three significant digits in the clinical trial report.

Adherence to the protocol will be assessed by the trial team. Important protocol deviation (IPD) categories will be suggested in the integrated Quality and Risk Management Plan (IQRMP). IPDs will be identified no later than in the Report Planning Meeting, and the IPD categories will be updated as needed.

All analyses will be based on the actual treatment group. Details will be specified in the TSAP.

Patients without any post-randomization data will be handled as missing for the respective endpoints and assessments (see [Section 7.3](#)).

Handling of anticipated problems (e.g. planned data transformations based on the expected distributional characteristics or convergence of the mixed models) will be addressed in the TSAP.

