7. PLANNED ANALYSIS

Unless otherwise specified, all analyses described in this section will be done on the Treated Set. The labelling and display format of statistical parameters will follow BI standards ([10](#)). For End-Of-Text (EoT) tables, the set of summary statistics is: N / Mean / SD / Min / Median / Max.

In descriptive statistics tables, mean, SD and median will be rounded to one additional digit than the raw individual value. In case some endpoints show some extreme data outside the expected range, quartiles and percentiles will be presented additionally.

Tabulations of frequencies for categorical data will include all possible categories and will display the number of observations in a category as well as the percentage (%) relative to the respective treatment group (unless otherwise specified, all patient in the respective subject set whether they have non-missing values or not). The precision for percentages should be one decimal point. The category missing will be displayed only if there are actually missing values.

Unless otherwise specified, all analyses will be provided by randomized treatment group (placebo or nintedanib) and overall (total).

[figure not shown]
For efficacy and safety end point analyses by time point, as well as for the safety analyses of Part A, patients switching during Part A to Part B will be censored at the time point of the switch and for the safety analyses of Part A (due to the definition of the double-blind period). Patients who started directly in Part B will be analyzed as a separate cohort, in addition to those randomized to nintedanib and those randomized to placebo.

[figure not shown]
All analyses performed after DBL1 will be repeated after DBL2 to include newly emerging data.

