7.5.2.1 Continuous (change from baseline) endpoints

The continuous secondary endpoint analysis will be based on the TS (according to randomised treatment), using available data from all visits (after time-windowing) from Part A and Part B and the estimate and contrast between treatments at the applicable endpoint visits will be used.

The analysis of continuous secondary endpoints is a restricted maximum likelihood (REML) based approach using a Mixed effect Model for Repeated Measures (MMRM). The analysis will include the fixed, categorical effects of treatment at each visit, age-group and the fixed continuous effects of baseline at each visit. Visit will be treated as the repeated measure with an unstructured covariance structure used to model the within-patient measurements.

Patients will be analyzed according to the age group stratum to which they belong to based on the data entered in the eCRF, which may not necessarily coincide with data used for randomisation.

The Kenward-Roger approximation will be used to estimate denominator degrees of freedom and adjust standard errors. Significance tests will be based on least-squares means (two-sided 95% confidence intervals will be presented). The primary treatment comparison will be the contrast between treatments at the endpoint visit.

In the event of non-convergence, the following methods will be attempted (in order) to overcome it:

1. Add the ‘singular=1e-10’ option in the model statement – This raises the threshold at which columns are declared linearly dependent (from typically 1e-12).
2. Set ‘maxiter=100’ in the Proc Mixed statement – This increases the number of convergence iterations used from a default of 50.
3. Set ‘scoring=4’ to specify use of the Fisher scoring algorithm in the first 4 iterations.
4. Exclude all visits > 24 weeks and report weeks > 24 data only descriptively (ANOVA) using observed data.
5. Include the statement ‘performance nothread’ – this removes multi-threading from the calculations.
6. Provide starting values for covariance parameters using a ‘parms’ statement. Estimates will be obtained from using a simpler covariance matrix.
7. Should none of the previous methods work, the covariance matrix will be changed from unstructured to Toeplitz with heterogeneous variances (TOEPH). Should this also not converge, a standard Toeplitz matrix (TOEP) will be fitted. Finally, if convergence still does not occur, then an order-1 autoregressive matrix (AR(1)) will be fitted.

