7.8 SAFETY ANALYSIS

7.8.1 Adverse Events

Adverse events will be coded using the current Medical Dictionary for Regulatory Activities (MedDRA) version in use at BI at the time of database lock. The analyses of AEs will be descriptive in nature.

All analyses of AEs will be based on the number of patients with AEs and NOT on the number of AEs. To account for the variable length of exposure to treatment in both study periods tables will be presented including count and percentage of patients with AE and the incidence rates of AEs with time at risk and rate per 100 patient years. Please refer to [Section 7.8.1.1](#) for further details on the derivation of time at risk and exposure-adjusted incidence rates.

Since this study consists of a double-blind, placebo-controlled part and an open-label part with nintedanib treatment only, three treatment periods will be used for analysis and definition of “treatment-emergent”:

- 1. Double-blind period:** Analyses of AEs will be presented by treatment group and overall. Only adverse events with onset or worsening on or after date of treatment start until end of double-blind period (defined as the day before first intake of open-label nintedanib or last double-blind drug intake + residual effect period, whichever is earlier) will be considered as treatment-emergent and will be included in the analysis. Adverse events will be counted under the treatment as randomized for the double-blind period.
- 2. Nintedanib exposure period:** Analyses of AEs will be presented by randomized treatment group and overall. All adverse events with onset or worsening on or after first intake of nintedanib (double-blind or open-label period) until last intake of nintedanib (double-blind or open-label period) + residual effect period will be considered as treatment-emergent and will be included in the analysis.

3. Over the whole-trial: Analyses of AEs will be presented by treatment group and overall. All adverse events with onset or worsening on or after date of treatment start until last drug intake + residual effect period will be considered as treatment-emergent and will be included in the analysis. Adverse events will be counted under the treatment as randomized for the double-blind period.

In case an AE starts on first day of open-label treatment, it is assigned to the open-label period (and not to the double-blind period).

For further details on summarization of AE data, please refer to ([8](#), [17](#)).

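### Protocol 7.2.1 calls for analysis by actual treatment, but the SAP counts double-blind adverse events, including the primary safety endpoint, by randomised treatment and shows no as-treated safety rule

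*Protocol*

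**What the plan says.** Protocol 7.2.1 gives one rule for every analysis: "All analyses will be based on the actual treatment group". It then adds: "Details will be specified in the TSAP". Protocol 7.2.2, 7.2.3 and 7.2.5 give no different rule for any class of endpoint.

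The SAP uses the other rule wherever it names one for comparing arms:

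- **Default (SAP 7):** tables are by randomised arm unless something else is specified. In its words, "all analyses will be provided by randomized treatment group (placebo or nintedanib) and overall (total").
- **Adverse events, double-blind period (SAP 7.8.1):** "Adverse events will be counted under the treatment as randomized for the double-blind period". SAP 5.1 and 7.4.1.2 define the primary safety endpoint on this period and refer to the same section.
- **Adverse events, nintedanib exposure period (SAP 7.8.1):** events are selected by real intake: "All adverse events with onset or worsening on or after first intake of nintedanib (double-blind or open-label period) until last intake of nintedanib" (plus the residual effect period). The columns, however, remain randomised: "Analyses of AEs will be presented by randomized treatment group and overall".
- **Efficacy (SAP 7.5.2.1 and 7.5.2.2):** the MMRM and the Kaplan-Meier displays follow the randomised arm.

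The visible SAP contains no rule that places a child's safety data under the drug actually received in Part A.

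**The concern.** The two documents assign patients to columns differently, and the difference reaches a primary endpoint. Protocol 3.2 justifies the placebo arm by the need to interpret adverse event reports. A safety table serves that purpose when each event sits under the drug the child was taking.

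Under the SAP rule, a placebo-randomised child who is given a nintedanib kit has drug events counted under placebo. A nintedanib-randomised child who is given a placebo kit has placebo-time events counted under nintedanib. With a planned placebo arm of about 10, a single child is a large share of the denominator.

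The opportunity exists. The Flow Chart has drug dispensed at Visits 2, 3, 4 and 5 in Part A, and Protocol 4.1.4 adds reserve wallets and unscheduled visits for dose reduction or smaller capsules. The documents report no such error, and treatment is assigned through the interactive response system.

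**Working it through.** **Text comparison.** Protocol 7.2.1 says actual treatment for all analyses. SAP 7 (default) and SAP 7.8.1 (adverse events) say randomised treatment. For a child who takes only the assigned drug, the two rules give the same column. They part only when a child receives the other arm's drug.

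**Inputs.** The Protocol synopsis plans about 20 nintedanib and 10 placebo patients. The documents give no expected adverse event rates, so the event counts below are assumed, to show the range.

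**Case A: one placebo-randomised child takes nintedanib and has the event.** Let x be the number with the event among the other 9 placebo children, and y the number among the 20 nintedanib children. The whole child is moved to the column of the drug taken.

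- Placebo: as randomised (x+1)/10, as treated x/9. The change is (9 − x)/90, at most 9/90 = 10.0 points (x = 0).
- Nintedanib: as randomised y/20, as treated (y+1)/21. The change is (20 − y)/420, at most 20/420 = 4.8 points (y = 0).
- The between-arm difference changes by the sum of the two.

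| x, y | As randomised: placebo vs nintedanib (difference) | As treated: placebo vs nintedanib (difference) | Change in difference |
|---|---|---|---|
| 0, 6 | 1/10 = 10.0% vs 6/20 = 30.0% (20.0) | 0/9 = 0.0% vs 7/21 = 33.3% (33.3) | 13.3 |
| 2, 12 | 3/10 = 30.0% vs 12/20 = 60.0% (30.0) | 2/9 = 22.2% vs 13/21 = 61.9% (39.7) | 9.7 |
| 4, 14 | 5/10 = 50.0% vs 14/20 = 70.0% (20.0) | 4/9 = 44.4% vs 15/21 = 71.4% (27.0) | 7.0 |
| 7, 18 | 8/10 = 80.0% vs 18/20 = 90.0% (10.0) | 7/9 = 77.8% vs 19/21 = 90.5% (12.7) | 2.7 |
| 9, 20 | 10/10 = 100% vs 20/20 = 100% (0) | 9/9 = 100% vs 21/21 = 100% (0) | 0 |

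**Case B: one nintedanib-randomised child takes placebo and has the event.** Let y be the number with the event among the other 19 nintedanib children, and x the number among the 10 placebo children.

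- Nintedanib: (y+1)/20 against y/19. The change is (19 − y)/380, at most 19/380 = 5.0 points.
- Placebo: x/10 against (x+1)/11. The change is (10 − x)/110, at most 10/110 = 9.1 points.

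**Case C: the child in Case A has no event.** The placebo percentage goes from x/10 to x/9, a change of x/90. The ceiling is again 10.0 points (x = 9), with the opposite sign.

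The ceilings are therefore 10 points for placebo and 5 for nintedanib, and the direction depends on who was misplaced and whether that child had the event.

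**The case against.** The strongest reply is that one rule would be used in practice. Protocol 7.2.1 leaves details to the SAP, and the SAP (final 09 March 2022) is later than Amendment 2 (14 June 2021). A reader might infer from the conflict that two rules are in force at once. The documents do not support that: the programmers would most likely follow the SAP. What stands is that reversing the rule is more than a detail, and that the SAP's rule is the less suitable one for safety.

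A reader might also infer that the departure was never declared, or that mis-dispensing is handled nowhere. Neither can be said. SAP 4.2, on changes, has a heading but no text in the public copy. SAP 6.2 places the handling of important protocol deviations in a specification that is not supplied.

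The nintedanib exposure tables are a fair partial answer, since a placebo-randomised child given nintedanib would enter them from the first intake. But that child would sit in the randomised-placebo column and the total, and these tables are not the primary safety analysis.

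Finally, a reader might take the protocol sentence to mean that the efficacy comparison will abandon randomisation. The SAP already analyses efficacy by randomised arm, so only the protocol wording is at issue there.

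**Conclusion.** The conflict is real and touches the primary safety endpoint, but its effect is contingent and the point is minor. If a child in Part A receives the other arm's drug, the visible SAP rule attributes events to a treatment not taken. The ceiling for one such child is 10 points on the placebo percentage and 5 on the nintedanib percentage.

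It would be tempting to read the 10 points as the expected effect on the headline result. They are a conditional maximum. The primary endpoint is any treatment-emergent adverse event. If most children have one, the misplaced child included, the between-arm difference moves by about 3 points, and by nothing if all do. Larger shifts are more plausible for individual uncommon terms. Without a cross-arm kit error there is no effect.

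The size rests on the planned arm sizes, assumed event counts, a single misallocated child, and reassignment of the whole child. The conflict does not touch the PK endpoint, which SAP 7.4.1.1 normalises by the dose actually taken.

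**What to change.** - **SAP 7 and 7.8.1:** state that adverse events and all other safety outputs for the double-blind period are tabulated by treatment actually received.
- **Mixed exposure:** add a rule, because one wrong kit may cover only the interval between two dispensing visits, about 2 to 12 weeks. For example, any nintedanib intake in Part A places the child's events from first nintedanib intake in the nintedanib column. State the denominators and time at risk on the same basis, since SAP 7.8.1 also reports rates per 100 patient-years. SAP 6.1 already uses the date of first nintedanib intake, so no new data are needed.
- **Efficacy:** keep the MMRM and Kaplan-Meier analyses by randomised arm, as the SAP already does.
- **Protocol 7.2.1:** align the sentence at the next amendment, or record the change in SAP 4.2 if that section does not already do so.

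The cost is a few sentences of text and a treatment-received variable in the safety datasets. If no kit error occurs, the double-blind tables are unchanged.

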7.2.2 Primary endpoint analyses

For the primary PK analysis, the area under the plasma concentration-time curve at steady state ($AUC_{\tau,ss}$) will be calculated by non-compartmental as well as compartmental analysis and descriptive statistics will be provided as detailed in [Section 7.2.1](#).

For patients receiving nintedanib in Part A, PK profiles on week 2 and week 26 are planned to be collected. For the primary endpoint $AUC_{\tau,ss}$ the $AUC_{\tau,ss}$ at week 2 will be used. If the week 2 value is missing, then it will be replaced by available $AUC_{\tau,ss}$ at week 26. For patients receiving placebo in Part A and nintedanib in Part B, $AUC_{\tau,ss}$ evaluated based on PK profiles at week 26 will be used (which corresponds to week 2 on active treatment). Further details on the PK analysis will be specified in the TSAP.

The primary safety endpoint listed in [Section 2.1.2](#) will be derived according to BI standards. For the primary analysis, only treatment emergent AEs during the double-blind period until week 24 will be included. The analysis will be based on the TS and will be descriptive in nature.

Subgroup analyses will be specified in the TSAP.

7.2.3 Secondary endpoint analyses

Analysis of secondary endpoints listed in [Section 2.1.3](#) will be descriptive in nature using a mixed model with repeated measurements (MMRM) for continuous endpoints. Time-to-event endpoints will be displayed descriptively using the Kaplan-Meier method. Categorical endpoints, safety and tolerability will be displayed descriptively in frequency tables. Further details will be provided in the TSAP.

7.2.5 Safety analyses

Adverse events will be coded using the Medical Dictionary for Drug Regulatory Activities (MedDRA). Standard BI summary tables and listings will be produced. All adverse events with an onset between start of treatment and end of the REP, a period of 28 days after the last dose of trial medication, will be assigned to the on-treatment period for evaluation.

All treated patients will be included in the safety analysis. In general, safety analyses will be descriptive in nature and will be based on BI standards. No hypothesis testing is planned.

Statistical analysis and reporting of adverse events will concentrate on treatment-emergent adverse events, i.e. all adverse events occurring between start of treatment and end of the REP. Adverse events that start before first drug intake and deteriorate under treatment will also be considered as 'treatment-emergent'.

As this study consists of a double-blind, placebo-controlled part (Part A) and an open-label part (Part B), two treatment periods will be used for analysis and definition of ‘treatment-emergent’:

1. Double-blind period: Only adverse events assigned to the on-treatment period with onset during the double-blind period will be considered for the analysis.
2. Whole-trial period: All adverse events assigned to the on-treatment period will be considered for the analysis.

Frequency, severity, and causal relationship of adverse events will be tabulated by system organ class and preferred term after coding according to the current version of the Medical Dictionary for Drug Regulatory Activities (MedDRA) at database lock.

Laboratory data will be analysed both quantitatively as well as qualitatively. The latter will be done via comparison of laboratory data to their reference ranges. Values outside the reference range as well as values defined as clinically relevant will be summarised. Treatment groups will be compared descriptively with regard to distribution parameters as well as with regard to frequency and percentage of patients with abnormal values or clinically relevant abnormal values.

Vital signs, physical examinations, or other safety-relevant data observed at screening, baseline, during the course of the trial and at the end-of-trial evaluation will be assessed with regard to possible changes compared to findings before start of treatment.

